7.1.13. Nerve Conduction Studies

Nerve conduction studies (NCS) will be performed at baseline and each evaluation visit. NCS will be performed on the left leg unless focal skin or orthopedic lesions preclude safe or accurate performance of NCS in this limb, in which case NCS will be performed on the right leg. NCS of the Sural sensory and Peroneal motor nerves with distal latency/conduction velocity, Peroneal motor conduction velocity in the leg segment (between the ankle and knee).

Definition of CSPN: For the purposes of CSPN diagnosis, an absent or low amplitude sural sensory response is required (as defined below).

Detailed protocol: NCS will be performed using standard techniques. Unless there is a local process such as a skin lesion, prior traumatic injury, history of radiculopathy etc. Skin temperature must be maintained > 31°C. Temperature should be recorded from the dorsal foot and documented. T

The sural sensory response will be performed in an antidromic fashion with stimulation 14 cm proximal to the recording electrode, which will be placed posterior to the lateral malleolus. Subsequently, two additional responses will be recorded using a sweep speed of 2 msec/division and an appropriate sensitivity setting. Three responses will be averaged using the same sweep and gain settings, from which amplitude and distal latency will be derived.

The peroneal motor response will be recorded from the EDB muscle with stimulation 9 cm proximally at the ankle, and at the level of the fibular head. Obtain a single waveform at each stimulation site, marking the onset latencies and baseline to peak amplitudes. The conduction velocity will be calculated. The minimal F wave latency will be measured using a sensitivity of 200-500 uV/division and at least 10 stimuli.

The waveforms will be uploaded to the central NCS laboratory at the University of Utah for immediate review. This review will ensure adequate adherence to protocol (temperature, stimulation location, averaging) and technical quality (baseline stability, absence of artifact). If after review, technical deficiencies are noted, the site will be notified and the selected NCS will be repeated⁵¹.

7.1.14. Skin Biopsy

The left leg is the preferred site for skin biopsy. The left lower extremity will be evaluated by study staff to rule out previous surgery at the hip or proximal to the knee. The site of biopsy should not have scarring, rash, burns, significant edema, or tattoos. If any of these conditions are present, the right leg should be similarly evaluated, and biopsied, if appropriate. All biopsies should be performed from the same side throughout the study, unless reasonable justification is documented (ie: trauma or surgery to previously used side).

A 3mm punch biopsy will be taken from the selected the biopsy site using local anesthesia (lidocaine with epinephrine) using standardized techniques. The punch will be placed in fixative and shipped overnight courier to the Utah Cutaneous Nerve Laboratory, where the tissue will be processed and stained using PGP9.5 and intraepidermal nerve fiber density (IENFD) measured⁶².

Details of the skin biopsy procedure, sample handling, processing and shipping are available in the reference manual for skin biopsy.

7.1.14.1. Distal Thigh Skin Biopsy

A distal thigh skin biopsy is collected at the following visits: Baseline (Visit 02), Week 32 (Visit 04), Week 64 (Visit 06), and Week 96 (Visit 08/Termination) and/or Early Termination.

A 3mm punch biopsy will be taken from the distal, lateral thigh 10 cm distal to superior margin of the patella.

Refer to the *Reference Manual for skin punch biopsy*.

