NTSS-6	Neuropathy Total Symptom Score – 6
PPI	Protocol Principal Investigator
PLP	Paraformaldehyde Lysine Phosphate
PSC	Protocol Steering Committee

NN108 Topiramate as a Disease Modifying Therapy for CSPN

Version 8.0

Version date 8/8/2018

QOL	Quality of Life
QUICKI	Quantitative Insulin Sensitivity Check Index
RAPA	Rapid Assessment of Physical Activity
SAE	Serious adverse event
SD	Standard Deviation
SOA	Schedule of Activities
TUG	Timed Up and Go
UENS	Utah Early Neuropathy Scale

SYNOPSIS

Title: Topiramate as a Disease Modifying Therapy for Cryptogenic Sensory Peripheral Neuropathy in Metabolic Syndrome: The “TopCSPN Study”

Short Title: The TopCSPN Study

Primary Objective: Determine if oral topiramate slows progression of CSPN using intraepidermal nerve fiber density (IENFD) as a primary measure of axon loss and the Norfolk Quality of Life – Diabetic Neuropathy (NQOL-DN) as a measure of neuropathy related quality of Life.

Secondary Objective: Determine the patient focused clinical relevance of change in IENFD and other CSPN surrogate measures using measures of pain, QOL, balance and mobility.

Design and Outcomes: The TopCSPN study will consist of screening and baseline visits, safety and monitoring visits every 16 weeks, evaluation visits at 32 and 64 weeks, a 96-week end-of-treatment visit, and a final safety assessment visit following termination of study drug. Distal thigh IENFD and the NQOL-DN will serve as co-primary outcome measures.

Interventions and Duration: The proposed study is a 96-week double blind randomized placebo-controlled trial of topiramate at a target dose of 100 mg daily (50 mg twice daily) as a potentially disease modifying therapy for cryptogenic sensory peripheral neuropathy (CSPN). Randomized participants will return to the clinic for follow up visits every 16 weeks. Evaluation visits will occur at 0, 32, 64 and 96 weeks. Enrollment will occur over a 48-week period. Dropout is estimated to be 4% at 32 weeks, 8% at 64 weeks, and 12% at 96 weeks.

Sample Size and Population: After a screening period, a total of 125 male and female participants from 18 to 80 years of age, inclusive, will be enrolled into two treatment arms (topiramate 100 mg daily or matching placebo). Enrollment will be stratified by body mass index (BMI).

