3. STUDY DESIGN

This is a 96-week double blind randomized placebo-controlled trial of topiramate at a target dose of 100 mg daily (50 mg twice daily) as a potentially disease modifying therapy for CSPN. After a screening period, a total of 125 male and female subjects from 18 to 80 years of age, inclusive, will be enrolled into two treatment arms (topiramate 100 mg daily or matching placebo). Randomized subjects will return to the clinic for follow up visits on a regular basis. Enrollment will occur over a 48-week period. All subjects will be followed for 96 weeks.

The study will consist of screening and baseline visits, safety and monitoring visits every 16 weeks, evaluation visits at 32, 64, and 96 weeks, and a final safety assessment visit following termination of study drug. The figure below displays the anticipated recruitment schedule and number of evaluable subjects at each visit, accounting for 12% dropout over 96 weeks. A Schedule of Assessments associated with each visit is provided at the end of the protocol in Appendix A.

TopCSPN Visit Schedule

Months	0-6	7-10	11-14	15-18	19-22	23-26	27-30	31-34	35-38	39-42	43-48	Total
Screening		62	62	62								186
Baseline		41	42	42								125
Week 16			41	42	42							125
Week 32				40	40	40						120
Week 48					40	40	40					120
Week 64						38	38	39				115
Week 80							38	38	39			115
Week 96								36	37	37		110
Total Safety Monitoring		0	41	42	82	40	78	38	39	0	NA	360
Total Evaluation		41	42	82	40	78	38	75	37	37	NA	470

Assumptions:

- (1) One in three screened potential participants will fail screening
- (2) Participant attrition will be 4% at 8 month of follow-up, 8% at 16, and 12% at 24 month study completion

Participants will be seen for a screening visit, of which up to 30 days will be allotted to complete the screening assessments. After informed consent is obtained, the investigator will review inclusion/exclusion criteria with the participant, obtain a medical, family, and neurological history and perform a general medical and detailed neuromuscular physical examination including vital signs. Concomitant medications, including all nutritional, herbal and alternative therapies, will be recorded.

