6.4. Visit 02 Baseline (Day 0)

Participants who continue to meet all inclusion/exclusion criteria after screening will present to the clinic for the baseline visit. The baseline visit will be performed within 30 days of the screening visit. However, the investigator will review, date and initial the screening laboratory assessments to confirm participant eligibility for study participation prior to the baseline visit procedures. Therefore, adequate time must be provided for the laboratory results to be received from the central laboratory. The investigator or designee will again review the study inclusion/exclusion criteria and participant medical history, confirming that the participant meets criteria for study participation before randomization.

The following procedures will be performed at the baseline visit (this visit may take about 4 hours):

- Review Inclusion/Exclusion criteria.
- Obtain a medical, family, and neurological history to assess for possible exclusionary conditions. Medical histories should include baseline symptoms, ongoing illnesses, other chronic conditions, surgical history, review of currently used medications, as well as any other important information that may affect the conduct of the study. See section 7.1.3.

- Review concomitant medications, including all nutritional, herbal and alternative therapies. See section 7.1.4.
- Review interval medical history.
- Review adverse events.
- Perform vital sign measurements: blood pressure (systolic and diastolic), heart rate (beats/minute), and body temperature (°C). See section 7.1.6.
- Record weight (kg) and Body Mass Index (BMI).
- Perform an abbreviated Physical Examination, including visual field and fall risk assessment.
- Perform Functional and Mobility testing (6MWT, TUG, ABC Scale). See section 7.1.11.
- Perform nerve conduction studies. See section 7.1.13.
- Perform distal thigh skin biopsy. See section 7.1.14.
- Collect blood samples for routine hematology panel blood, basic metabolic panel, topiramate level and DNA analysis (OPTIONAL). See section 7.1.12.
- Collect urine for a urine pregnancy test (pregnancy test for women of child-bearing potential only).
- For women of childbearing potential and sexually active males, review acceptable birth control methods that must be used during the study.
- Perform subject randomization via interactive voice response system (IVRS) and/or interactive web response system (IWRS). See section 4.4.5.
- Dispense study drug.

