c. Analysis of Co-Primary Endpoints. We hypothesize that topiramate will reduce the rate of deterioration of IENFD over the full follow-up period. Hence the primary analysis of the IENFD will compare the mean IENFD slope between the treatment and control groups under a longitudinal model with fixed effects for baseline IENFD, age, baseline BMI randomization stratification group, follow-up time (as a continuous variable), and the interaction between treatment assignment and follow-up time. Inclusion of baseline IENFD as a covariate will increase statistical power in a similar fashion as adjustment for the baseline level of the outcome in a conventional analysis of covariance. Expressed mathematically, the longitudinal model for IENFD is: $Y_{it} = \alpha_0 + Y_{i0} \beta_0 + \text{Age} \beta_1 + [\text{BMI Group}] \beta_2 + Y_{i0} \times \text{time}_{ij} \times \beta_3 + T_i \beta_4 + \text{time}_{it} \beta_5 + T_i \times \text{time}_{it} \beta_6 + \varepsilon_{it}$, $\text{Var}(\varepsilon) = \Sigma$, $i = 1, 2, \dots, N$, $t = 0, 1, 2, 3$, where Y_{it} denotes the IENFD measurement for patient i at visit t , with $t = 0$ representing the baseline visit so that Y_{i0} is the baseline IENFD, T_i denotes the randomized treatment group for the i th patient (with $T_i = 1$ for the topiramate group, and $T_i = 0$ for the control group), time_{it} denotes the time of the t^{th} IENFD measurement for patient i , $T_i \times \text{time}_{it}$ denotes the treatment by time interaction, and the ε_{it} denote residuals of the IENFD measurements which are assumed to be normally distributed with a covariance matrix Σ which is described below. The coefficient β_6 represents the effect of the topiramate treatment on the mean IENFD slope over time. We will use a general unstructured covariance model for Σ ⁷⁶ so that the full model represents a special case of the linear mixed model^{76,77} that allows for all possible correlations among the residuals among the IENFD measurements. When the number of time points is small relative to the number of subjects as is the case for IENFD in this proposal, the general unstructured covariance model is widely used in randomized trials because it provides essentially identical statistical power to that obtained under less general covariance models while avoiding the need for post-hoc modifications to satisfy modeling assumptions⁷⁶. Estimates of the model coefficients and standard errors will be obtained by restricted maximum likelihood estimation (RMLE)⁷⁸.

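### The biopsy landmark in section 7.1.14.1 falls below the knee, although the same sentence and the co-primary endpoint name the distal thigh

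*Combined protocol and SAP*

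**What the plan says.** Section 7.1.14.1 gives the site and its landmark in one sentence: "A 3mm punch biopsy will be taken from the distal, lateral thigh 10 cm distal to superior margin of the patella". It then points to a reference manual for skin punch biopsy.

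Elsewhere the protocol is consistent about the site:

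- The synopsis defines the endpoint by it: "Distal thigh IENFD and the NQOL-DN will serve as co-primary outcome measures".
- The baseline list (section 6.4) reads "Perform distal thigh skin biopsy. See section 7.1.14". The lists for weeks 32, 64 and 96 and for early termination (sections 6.6, 6.8, 6.10 and 6.12) ask for the same biopsy, as do section 3 and Appendix A.
- Section 5.2 rests the dose rationale partly on earlier findings for thigh IENFD.
- Under section 7.1.14 the limb is first "evaluated by study staff to rule out previous surgery at the hip or proximal to the knee".

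Section 7.1.14 also requires the same side to be used throughout unless a change is justified, and defers procedural detail: "Details of the skin biopsy procedure, sample handling, processing and shipping are available in the reference manual for skin biopsy". The documents contain no other numeric biopsy landmark.

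**The concern.** The name and the measurement in section 7.1.14.1 point to different parts of the limb. An operator who measures as instructed samples the lower leg, which is not the stated co-primary endpoint. An operator who follows the name has no usable distance in the protocol.

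The primary IENFD contrast is a comparison of slopes. In section 10, item c, the treatment-by-time coefficient "represents the effect of the topiramate treatment on the mean IENFD slope over time". If the sentence were read differently at different visits for the same participant, the change of level would enter that participant's slope as extra variability. The protocol has a same-side rule but no same-level rule.

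Adherence is also unclear. Section 7.1.2 treats any activity not performed as the protocol outlines as a deviation. Read literally, every biopsy departs from one half of this sentence, so a monitor cannot say which biopsies comply.

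**Working it through.** The plan states no figure that can be reproduced for this point. The check is one of direction, then distance, then exposure.

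**1. Direction.** On a limb, distal means towards the foot. The superior margin of the patella is the top of the kneecap. A point any distance distal to it is at or below knee level. The thigh lies proximal to it. This conflict does not depend on any assumed measurement.

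**2. Distance.** Inputs: the 10 cm in section 7.1.14.1, and patella height *h*, which the documents do not give and which is assumed.

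Distance below the lower edge of the patella = 10 cm − *h*

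| Assumed *h* (cm) | Result (cm below the lower edge) |
|---|---|
| 3.5 | 10 − 3.5 = 6.5 |
| 5.5 | 10 − 5.5 = 4.5 |
| 6.0 (wider range) | 10 − 6.0 = 4.0 |

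For the point to lie no lower than the lower edge of the patella, *h* would have to be at least 10 cm. Even then the point would be at the knee and not on the thigh.

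**3. Exposure.** The visit table in section 3 gives the planned numbers at the four visits with a biopsy:

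125 (baseline) + 120 (week 32) + 115 (week 64) + 110 (week 96) = 470

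This matches the table's own evaluation total of 470. Biopsies at early-termination visits come on top. Section 4.4 gives 14 network sites and one other, so 14 + 1 = 15 sites. These are the scheduled biopsies that the sentence governs. They are not an estimate of misplaced ones.

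**4. Scale of the endpoint.** Section 10, item e, powers the trial for a slope difference of 0.47 fibers/mm/year. Over 96 weeks that is 0.47 × 96/52 = 0.87 fibers/mm. The Go/No-Go cut-offs in item f are 0.30 and 0.22 fibers/mm/year. Differences of this size leave little room for avoidable measurement noise. The documents give no IENFD values by anatomical level, so the noise that a change of level would add cannot be calculated.

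**The case against.** The best defence is that nobody would be misled. The section heading, the sentence itself, every visit list and Appendix A say thigh. Against them stands one directional word, which reads as a drafting slip. Procedural detail is deferred to a manual that may give a workable landmark, in which case the practical effect could be nil. A level held constant within a participant would not add visit-to-visit variability, and the model adjusts for baseline IENFD and its interaction with time. No misplaced biopsy has been shown.

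Much of this stands as a limit on the consequence. The intended site is clear, the harm is conditional, and 470 counts scheduled biopsies only. Two supporting points are also weak. The pre-biopsy limb check fits a site above the knee, but surgery above the knee could matter for a lower-leg site too. Section 7.1.13 describes central review of stimulation location for nerve conduction, and the text supplied describes nothing comparable for biopsy level; but the manual may contain such a check, so little can be built on the silence.

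None of this removes the contradiction. Sites that follow the name still lack a distance in the protocol, so the level could vary. If the manual is right, it contradicts the protocol, which still needs correcting. If the manual repeats the error, the problem is operational. A level held constant on the lower leg would still not be the named endpoint.

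**Conclusion.** The concern holds. The sentence contradicts itself whatever patella height is assumed. With an assumed height of 3.5 to 5.5 cm, the literal landmark is 4.5 to 6.5 cm below the lower edge of the patella; extending the assumption to 6 cm gives 4.0 to 6.5 cm.

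Confidence is high for the contradiction. It does not extend to an effect on the results: the number of below-knee biopsies, which may be none, and any change in the IENFD slope or its variance are unknown. The contradiction should be corrected because the sentence determines where co-primary endpoint tissue is taken and the correction is cheap.

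**What to change.** Reconcile the landmark in section 7.1.14.1 with the named site and with the skin-biopsy reference manual, so that it lies on the distal lateral thigh and both documents state the same one. The documents do not support a particular replacement distance, and none is proposed here. Send sites a memo with the reconciled wording. This costs a one-line protocol correction and a memo, with no new procedure.

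Then find out whether biopsy level was recorded. If it was, check for any biopsies taken below the knee and, if there are some, examine them in a sensitivity analysis of the IENFD slope. If it was not, say so in the report. This check is additional work, and the documents do not say whether the record exists. What the manual says and what sites were trained to do will show how much effort it deserves.

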7.1.15. Columbia-Suicide Severity Rating Scale (C-SSRS)

The C-SSRS is a suicidal ideation rating scale. It measures a Subject's degree of suicidal ideation on a scale ranging from wishing to be dead without an active plan to active suicidal ideation with a specific plan and intent to die. Only investigators who have been fully trained in the administration of the C-SSRS will assess subject suicidality. As part of training, investigators are prepared to respond to and manage instances in which patients express suicidal ideation or exhibit suicidal behavior.

7.1.16. The Norfolk Quality of Life – Diabetic Neuropathy (NQOL-DN) Scale

Patient reported neuropathy related QOL. The NQOL-DN is a validated neuropathy specific QOL measure. Factor analysis has been used to group NQOL-DN items into 6 subscores: symptoms, autonomic, small fiber, large fiber, and activities of daily living²⁷.

7.1.17. The Rapid Assessment of Physical Activity (RAPA) Survey

The RAPA is a validated patient reported survey that quantifies the intensity and frequency of aerobic and strength activity.⁹⁰ The RAPA is included in order to assess the degree of exercise

and physical activity between the treatment groups. This is important because intensive exercise programs may impact the natural history of CSPN associated with prediabetes.

7.1.18. Subject Adherence Assessments

At each study visit, the site Investigator and/or Study Coordinator will assess the subject's compliance with the study requirements by performing study drug reconciliation and collecting study drug containers. This will also include reviewing protocol compliance, including use of study drug and concomitant medications. If applicable, subjects who fail to comply with the study requirements may be removed from the study.

The site Investigator and/or Study Coordinator will conduct monthly telephone calls between clinic visits (i.e.: between Baseline and Week 16 calls should occur at Week 4, Week 8, and Week 12) to encourage protocol compliance and enhance retention.

7.1.19 Optional Tissue Banking

DNA samples will be collected at Baseline using supplies provided by URM. Centrifuge the EDTA tube at 1500 RPM for 15 minutes. The buffy coat will be transferred into cryovials provided by Utah and stored at -80C. At the end of the enrollment period, sites will batch ship all the buffy coat samples to Utah with shipment kit and air bills provided.

Skin biopsy tissue collected for IENFD testing for will be stored at the Utah Cutaneous Nerve Lab until study closure. Samples from participants who consent to long-term tissue storage will be placed in long-term tissue banking and the rest will be destroyed.

The DNA and tissue bank will be located in the laboratory of [name], at the University of Utah. Participants can withdraw consent to bank their samples by notifying their CSS investigator. Banking preferences will be entered into the EDC by the CSS staff. At the end of the study, DNA or tissue in the bank will be destroyed if participants opt out of banking at any time during the study or do not mark and initial their preference on the consent form.

8. MANAGEMENT OF ADVERSE EVENTS

Extensive data regarding safety and adverse events are available from clinical trials of topiramate for epilepsy and episodic migraine. The dose of topiramate to be used in the TopCSPN Study is similar to that used for episodic migraine (50-200mg daily). Adverse events observed in randomized trials for migraine will be summarized⁶⁵. Following this summary, potentially significant adverse events observed at higher doses will be listed.

When topiramate must be discontinued for participant safety, the dose can be stopped immediately or titrated down based on the clinical judgement of the site investigator.

Adverse Events Observed at 100 mg daily of topiramate:

- Anorexia. Loss of appetite is one of the mechanisms contributing to weight loss. Most commonly anorexia is mild. In subjects complaining of intolerable anorexia, the dose will be tapered to the maximal tolerated dose.
- Fatigue. Subjects complaining of intolerable fatigue will be asked to taper the dose to the maximum tolerated.
- Memory Problems. Topiramate may cause confusion, psychomotor slowing, poor concentration, or memory loss. These symptoms are more commonly observed with rapid dose escalation. Patients complaining of intolerable memory problems, or those observed to have cognitive dysfunction sufficiently significant to warrant dose modification in the opinion of the PI will taper their dose to that maximally tolerated.
- Nausea. Subjects complaining of intolerable nausea will be asked to taper the dose to the maximum tolerated.
- Paresthesias. Paresthesias are typically mild and uncommonly lead to discontinuation. In the setting of this study, paresthesias may also be related to the underlying disease (CSPN), or nerve regeneration. There are no data suggesting topiramate causes or worsens peripheral neuropathy. Subjects experiencing increased paresthesias will be encouraged to continue to participate unless the symptom is severe enough in the opinion of the PI to warrant dose reduction.

Potentially serious adverse events noted in the package insert include:

- Glaucoma. Topiramate has been reported to cause acute myopia associated with secondary angle closure glaucoma. Symptoms typically occur within 1 month of initiating therapy, and include decreased visual acuity and ocular pain. Ophthalmologic findings can include myopia and ocular hyperemia (redness). Mydriasis may or may not be present. Visual acuity will be assessed at each visit and subjects with reduced acuity, ocular pain, or ocular hyperemia will discontinue medication and be immediately referred for ophthalmologic examination.
- Kidney stones. 1.5% of adults exposed to topiramate during its adjunctive epilepsy therapy development reported the occurrence of kidney stones, an incidence about 2 to 4 times greater than expected in a similar, untreated population. Carbonic anhydrase inhibitors (Topiramate, but also zonisamide, acetazolamide or dichlorphenamide) can promote stone formation by reducing urinary citrate excretion and by increasing urinary pH.
- Metabolic acidosis. Hyperchloremic, non-anion gap, metabolic acidosis (i.e., decreased serum bicarbonate below the normal reference range in the absence of chronic respiratory alkalosis) is caused by renal bicarbonate loss due to the inhibitory effect of topiramate on carbonic anhydrase. Renal disease, severe respiratory disorders, status epilepticus, diarrhea, and ketogenic diet may increase this risk. Symptoms may include hyperventilation, fatigue, anorexia, or rarely cardiac arrhythmias or stupor. Serum electrolytes including bicarbonate will be measured at each study visit. Subjects with a total bicarbonate of < 17 mEq/L and a > 5 mEq/L decrease from pretreatment will discontinue treatment.
- Oligohidrosis (decreased sweating) and subsequent loss of temperature regulation with hyperthermia has been reported in adults, especially in combination with carbonic anhydrase inhibitors and anticholinergic medications. Subjects complaining of significant reduction in sweating will taper medication to the maximum tolerated dose.
- Visual field defects (independent of elevated intraocular pressure) have been reported in clinical trials and in postmarketing experience. Visual fields will be assessed at each study

visit. Patients observed to have new visual field abnormalities will be referred for ophthalmologic examination and medication will be discontinued.

